### “3.3.2 Level of improvement in endoscopy findings ( ileocecum)”

Patients included in analysis: Patients included in efficacy analysis

Objective of analysis: Level of improvement in endoscopy findings (ileocecum) is shown by time of evaluation.

Analysis items: The number of patients included in analysis, the number of patients who achieved improvement in endoscopy findings and rate of these patients to those included in analysis should be calculated by the time of evaluation.

Notes: Patients with a check mark in a box “1.ileocecum” in a description about endoscopy before administration start in “Level of improvement in endoscopy findings” in the survey sheet should be included in analysis.

Time Allowance for the time of evaluation should be according to “12.4. Rate of patients who achieved clinical improvement, rate of patients who achieved complete remission, and time of evaluation of level of improvement in endoscopy findings”. Patients who have evaluation corresponding to Time Allowance of each time of evaluation should be included in analysis.

### “3.3.3 Level of improvement in endoscopy findings ( colon)”

Patients included in analysis: Patients included in efficacy analysis

Objective of analysis: Level of improvement in endoscopy findings (colon) is shown by time of evaluation.

Analysis items: The number of patients included in analysis, the number of patients who achieved improvement in endoscopy findings and rate of these patients to those included in analysis should be calculated by the time of evaluation.

Notes: Patients with a check mark in a box “2. colon” in a description about endoscopy before administration start in “Level of improvement in endoscopy findings” in the survey sheet should be included in analysis.

Time Allowance for the time of evaluation should be according to “12.4. Rate of patients who achieved clinical improvement, rate of patients who achieved complete remission, and time of evaluation of level of improvement in endoscopy findings”.

Patients who have evaluation corresponding to Time Allowance of each time of evaluation should be included in analysis.

#### “3.3.4 Level of improvement in endoscopy findings (esophagus)”

Patients included in analysis: Patients included in efficacy analysis

Objective of analysis: Level of improvement in endoscopy findings (esophagus) is shown by time of evaluation.

Analysis items: The number of patients included in analysis, the number of patients who achieved improvement in endoscopy findings and rate of these patients to those included in analysis should be calculated by the time of evaluation.

Notes: Patients with a check mark in a box “3. esophagus” in a description about endoscopy before administration start in “Level of improvement in endoscopy findings” in the survey sheet should be included in analysis.

Time Allowance for the time of evaluation should be according to “12.4. Rate of patients who achieved clinical improvement, rate of patients who achieved complete remission, and time of evaluation of level of improvement in endoscopy findings”. Patients who have evaluation corresponding to Time Allowance of each time of evaluation should be included in analysis.

#### “3.4 Aggregation of efficacy by patient characteristics”

Patients included in analysis: Patients included in efficacy analysis

Objective of analysis: As primary survey item, efficacy ratio in level of improvement at the last follow-up for factor analysis.

Analysis items: The number of patients included, the number of responding patients regarding level of overall improvement (significant improvement and improvement) and rate of these patients to those included in analysis, the number of patients who showed ineffectiveness in level of overall improvement and rate of these patients to those included in analysis, and test provided for effectiveness (Fisher’s exact test for nominal scale factors, and Mann-Whitney u test for ordinal scale factors) were calculated by following patient characteristics.

Notes: Patient characteristics are as follows:

Age (years), sex, disease duration (years), complication, hepatic function disorder as complication, renal impairment as complication, medical history, allergy history, smoking habit, self-administration as administration status of this drug, previously used drug/previous treatment, biological preparation adalimumab as previously used drug, biological preparation infliximab as previously used drug, steroid as previously used drug, immunomodulative drug as previously used drug, immunosuppressive drug as

previously used drug, oral adrenocortical steroid as concomitant drug, oral mucosa recurrent aphthous ulcer as main symptoms of Behcet disease other than gastrointestinal symptoms, cutaneous symptoms as main symptoms of Behcet disease other than gastrointestinal symptoms, eye symptoms as main symptoms of Behcet disease other than gastrointestinal symptoms, ulcer of vulva as main symptoms of Behcet disease other than gastrointestinal symptoms, arthritis without deformity or rigidity as accessory symptoms of Behcet disease other than gastrointestinal symptoms, epididymitis as accessory symptoms of Behcet disease other than gastrointestinal symptoms, vascular lesion as accessory symptoms of Behcet disease other than gastrointestinal symptoms, moderate or higher degree central nervous lesion as accessory symptoms of Behcet disease other than gastrointestinal symptoms, diagnostic classification of Behcet disease, days until the last date of the administration, and mean daily dose.

#### “3.5.1 Main symptoms of Behcet disease”

Patients included in analysis: Patients included in efficacy analysis

Objective of analysis: Presence or absence of main symptoms of Behcet disease is shown by time of evaluation.

Analysis items: The number of patients included in analysis, the number of patients with Behcet disease by main symptoms and rate of these patients to those included in analysis should be calculated by time of evaluation.

Notes: Time Allowance at time of evaluation should be according to “12.6 Time of evaluation of main and accessory symptoms of Behcet symptoms”. Patients who have evaluation corresponding to Time Allowance of each time of evaluation should be included in analysis.

#### “3.5.2 Accessory symptoms of Behcet disease”

Patients included in analysis: Patients included in efficacy analysis

Objective of analysis: presence or absence of accessory symptoms of Behcet disease is shown by time of evaluation.

Analysis items: The number of patients included in analysis, the number of patients with Behcet disease by accessory symptoms and rate of these patients to those included in analysis should be calculated by the time of evaluation.

Notes: Time Allowance at time of evaluation should be according to “12.6 Time of evaluation of main and accessory symptoms of Behcet symptoms”. Patients who have evaluation corresponding to Time Allowance of each time of evaluation should be included in analysis.

### “3.6 Changes in CRP levels”

Patients included in analysis: Patients included in efficacy analysis

Objective of analysis: Measurement of CRP levels is shown by time of evaluation.

Analysis items: Summary statistics of CRP (the number of patients, mean value, standard deviation, the minimum, median, maximum value) should be calculated by time of evaluation.

Notes: Time Allowance at time of evaluation should be according to “12.7 Time of evaluation of changes in CRP levels”. Patients who have evaluation corresponding to Time Allowance of each time of evaluation should be included in analysis.

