### 10.3. Efficacy analysis

Name of data	Derivation and calculation method
Level of overall improvement	Description of level of overall improvement in the survey sheet (assessment provided by attending physician) should be employed.
Clinical improvement	Patients with the level of improvement in endoscopy findings in the survey sheet of “2. shrinkage” or lower and comprehensive evaluation of gastrointestinal symptoms in the survey sheet of “1” or lower (0, 1) are assessed as patients with clinical improvement.
Complete remission	Patients with the level of improvement in endoscopy findings in the survey sheet of “1. remission or scar” and comprehensive evaluation of gastrointestinal symptoms in the survey sheet of “0” are assessed as patients with complete remission.
Improvement in gastrointestinal symptoms (abdominal pain, diarrhoea, other gastrointestinal symptoms)	If comprehensive evaluation of gastrointestinal symptoms or evaluation of each gastrointestinal symptom differs by 1 point or higher compared to those at the start of the administration of this drug (points of evaluation at the start of administration - those at each evaluation $\geq$ 1), patients are assessed as those who obtained improvement.

Name of data	Derivation and calculation method
Level of improvement in endoscopy findings	Description in “level of improvement in ulcer with the maximum diameter” in the level of endoscopy findings in the survey sheet should be employed.
Main symptoms and accessory symptoms of Behcet disease	Description in evaluations for each main and accessory symptom in efficacy evaluation in the survey sheet should be employed. “0” should be defined as “no symptom”, “1,2,3” should be defined as “there are any symptoms”, unknown or not described data should be defined as “unknown/not described”
CRP	Measurement in the survey sheet should be employed. If measurement is undetectable, the measurement should be deemed as undetectable limit.

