#### 12.7. Changes in CRP levels

Time Allowance at evaluation when the start date of the initial administration of this drug is defined as 1 is as follows:

Time of evaluation	Time Allowance(Day)
Administration start	-14-1(record date is day 1)
24 weeks after the administration start	155-183 (record date is day 169)
52 weeks after the administration start	351-379 (record date is day 365)
76 weeks after the administration start	505-561 (record date is day 533)
104 weeks after the administration start	701-757 (record date is day 729)
128 weeks after the administration start	869-925 (record date is day 897)
156 weeks after the administration start	1065-1121 (record date is day 1093)

The data on the closest day to the record date should be included in analysis and if there is multiple data for the same day, data with the worse value should be included in analysis.

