Notes: The number of patients should be that of patients with data of evaluation of endoscopy findings within relevant period subject to analysis and evaluation of gastrointestinal symptoms in 4 weeks before and after the date of implementation of endoscopy. Time Allowance for the time of evaluation should be according to “12.4. Rate of patients who achieved clinical improvement, rate of patients who achieved complete remission, and time of evaluation of level of improvement in endoscopy

findings”.

“3.2.1 Comprehensive evaluation of gastrointestinal symptoms at each time of evaluation”

Patients included in analysis: Patients included in efficacy analysis

Objective of analysis: Comprehensive evaluation of gastrointestinal symptoms is shown by time of evaluation.

Analysis items: The number of patients included in analysis, the number of patients have comprehensive evaluation of gastrointestinal symptoms (0,1,2,3,4) and rate of these patients to those included in analysis, the number of patients who achieved improvement in gastrointestinal symptoms and rate of these patients to those included in analysis should be calculated by time of evaluation.

Notes: Time Allowance at time of evaluation should be according to “12.5 Time of evaluation of gastrointestinal symptoms”. Only patients who have evaluation corresponding to administration start and Time Allowance of each time of evaluation should be included in analysis.

“3.2.2 Evaluation of gastrointestinal symptoms at each time of evaluation”

Patients included in analysis: Patients included in efficacy analysis

Objective of analysis: Evaluation of gastrointestinal symptoms is shown by time of evaluation.

Analysis items: The number of patients included in analysis, the number of patients who have evaluation of gastrointestinal symptoms (0,1,2,3,4) and rate of these patients to those included in analysis, the number of patients who achieved improvement in detailed classifications of gastrointestinal symptoms and rate of these patients to those included in analysis should be calculated by time of evaluation.

Notes: Time Allowance at time of evaluation should be according to “12.5 Time of evaluation of gastrointestinal symptoms”. Only patients who have evaluation corresponding to administration start and Time Allowance of each time of evaluation should be included in analysis.

“3.3.1 Level of improvement in endoscopy findings”

Patients included in analysis: Patients included in efficacy analysis

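### Table 3.6 is titled as changes in CRP but summarises levels in a shifting set of patients; a paired baseline-to-visit summary should be added

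*SAP*

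**What the plan says.** In SAP section 13.3 the table is headed "3.6 Changes in CRP levels". Its aim is stated as "Measurement of CRP levels is shown by time of evaluation", and the output is specified as "Summary statistics of CRP (the number of patients, mean value, standard deviation, the minimum, median, maximum value) should be calculated by time of evaluation". The inclusion rule is "Patients who have evaluation corresponding to Time Allowance of each time of evaluation should be included in analysis".

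Section 10.3 gives the derivation of CRP as "Measurement in the survey sheet should be employed", plus a rule for undetectable values. No change variable is defined. Section 12.7 sets an administration-start window of day -14 to day 1 and visit windows at weeks 24, 52, 76, 104, 128 and 156. Section 9.1 says missing data are not filled in unless an item-specific rule says so, and there is none for missing CRP.

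Tables 3.2.1 and 3.2.2 (gastrointestinal symptoms) use a different rule: "Only patients who have evaluation corresponding to administration start and Time Allowance of each time of evaluation should be included in analysis".

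**The concern.** The survey, as described in the SAP, has no comparator group, so a patient's own value at the start of treatment is the natural reference for CRP. Table 3.6 does not use it. It sets one cross-section beside another, and the title invites the reader to take the difference between them as change.

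That is safe only if the patients measured at each visit are alike in CRP level. The SAP shows three ways in which the measured group can alter:

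- **Planned follow-up.** Section 2 assigns 52, 104 or 156 weeks by start date.
- **Discontinuation.** Section 11 lists insufficient effect and adverse events among the reasons.
- **Missing values.** A patient with no value in the start window still enters later columns, so the later groups need not even be subsets of the baseline group.

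CRP is one of the efficacy items named in section 5.1, and section 3.1 says the results may go into the reassessment application. A shift in mean CRP caused by a shift in patients could be read there as an effect of treatment.

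**Working it through.** **Which patients can contribute (SAP sections 2 and 12.7)**

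| Cohort, by start date | CRP windows within planned follow-up |
|---|---|
| 16 Aug 2014 to 15 Aug 2015 (52 weeks) | start, 24, 52 |
| 16 Aug 2013 to 15 Aug 2014 (104 weeks) | start, 24, 52, 76, 104 |
| by 15 Aug 2013 (156 weeks) | start, 24, 52, 76, 104, 128, 156 |

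The week 76 and 104 columns lose the latest starters by design, and the week 128 and 156 columns keep only the earliest starters. Discontinuation and missing values come on top. The SAP does not say how much CRP is collected after discontinuation, and section 12.7 does not exclude such values.

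**How far the mean could move with no true change**

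The SAP states no CRP distribution, drop-out rate or within-patient correlation, so there is no plan figure to reproduce. All inputs below are assumptions:

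- CRP is log-normal with log-SD σ = 1.2, with the same distribution at start and visit.
- The within-patient correlation ρ on the log scale is 0.5, 0.7 or 1.0.
- 30% of patients are lost overall, split by whether baseline CRP is below or above its median.

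Let k_lo and k_hi be the proportions retained below and above the median. Patients above the baseline median contribute a share Φ(ρσ) of the visit mean, so

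observed visit mean / baseline mean = [k_hi Φ(ρσ) + k_lo (1 − Φ(ρσ))] / [(k_hi + k_lo)/2].

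The values of Φ(ρσ) are Φ(0.60) = 0.7257, Φ(0.84) = 0.7995 and Φ(1.20) = 0.8849.

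Example with 20% lost below the median, 40% above, and ρ = 0.5: (0.6 × 0.7257 + 0.8 × 0.2743)/0.7 = 0.6549/0.7 = 0.936, a false fall of 6.4%.

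Example with 10% lost below, 50% above, and ρ = 1.0: (0.5 × 0.8849 + 0.9 × 0.1151)/0.7 = 0.5460/0.7 = 0.780, a false fall of 22.0%.

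| Loss below / above median | ρ = 0.5 | ρ = 0.7 | ρ = 1.0 |
|---|---|---|---|
| 30% / 30% | 0% | 0% | 0% |
| 20% / 40% | 6.4% | 8.6% | 11.0% |
| 10% / 50% | 12.9% | 17.1% | 22.0% |
| 0% / 60% (extreme) | 19.3% | 25.7% | 33.0% |

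A simulation of 400,000 patients per scenario agrees to within half a percentage point. For the middle two rows the simulated median falls from 1.00 to between 0.93 and 0.71.

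**What pairing does**

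- *Loss depends on baseline CRP (middle two rows).* The median within-patient ratio in patients with both values is 1.00 at ρ = 1.0, rising to about 1.15 at ρ = 0.5 with 10%/50% loss. The false fall disappears, with some upward regression to the mean.
- *Loss depends on CRP at the visit itself (10%/50%, ρ = 0.5 to 0.7).* The unpaired median is 0.71 and the paired ratio is 0.86 to 0.92. Pairing reduces the bias but leaves part of it.

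**The case against.** The best defence is that the table does what its objective says: it shows levels by visit. Only the heading speaks of changes, and no passage tells anyone to draw a conclusion about change from it. The paired rule in Tables 3.2.1 and 3.2.2 is needed there because section 10.3 defines symptom improvement as a difference from the start score. Tables 3.5.1 and 3.5.2, which report status by visit, use the same available-case rule as Table 3.6. The plan therefore pairs where a difference is calculated and uses available cases where a status or level is shown. This stands: the available-case rule is not a slip against a uniform rule. The symptom tables show only that pairing is feasible within this plan.

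Three stronger readings are tempting, and the document does not support them.

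- *That each visit describes different patients.* The groups overlap; they are a changing set.
- *That patients with high CRP and poor response are the ones who leave.* Nothing in the SAP links discontinuation to CRP. Patient's request and not visiting are also listed reasons, and the loss of the shorter cohorts is administrative.
- *That the apparent fall would be near 30%.* A two-point example gives this. Half the patients stay at 2.0 mg/dL and half at 0.4, and 60% of the high group and none of the low group leave. The mean goes from 1.20 to (0.2 × 2.0 + 0.5 × 0.4)/0.7 = 0.857, a fall of 28.6%. That is one extreme assumed pattern.

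The table also prints the number of patients per visit, which makes attrition visible. It does not correct for it.

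**Conclusion.** The point holds as a mismatch between title and content. As specified, Table 3.6 cannot support a statement about change in CRP within patients, because differences between its columns mix change with composition. The shift in composition from planned follow-up is certain from the SAP wherever the shorter cohorts contain patients. Whether it biases CRP, by how much and in which direction cannot be told from the document.

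Under the assumptions above (log-normal CRP, log-SD 1.2, 30% loss, no true change), the false fall in the mean is 0% if loss is unrelated to baseline CRP and about 6% to 22% under moderate selection on it. Loss concentrated in low-CRP patients would push the mean the other way. A reader should not conclude that any fall seen in the table would be an artefact.

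Priority is minor. The table is descriptive, has no test or decision rule, and CRP is one of several efficacy items. The tested efficacy factor analysis (Table 3.4) uses overall improvement.

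**What to change.** Keep the current visit-wise summaries and add a paired block to Table 3.6. For each visit, restrict to patients with both an administration-start value (day -14 to 1) and a value in the visit window, and report:

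- the number of patients;
- baseline CRP, visit CRP, and change or ratio, each with median and quartiles, since CRP is likely to be skewed. Quartiles are already in the SAP section 2 definition of summary statistics but are not in the list for this table.

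Add a matching change (or ratio) variable to section 10.3. Preferably also show the block by 52-, 104- and 156-week cohort, so that the planned loss of patients is separated from discontinuation.

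The cost is a few columns from variables and windows the plan already defines. Patients without a baseline CRP drop out of the paired part, so its numbers will be smaller. A footnote should say that the paired result describes patients still measured at that visit, and that pairing does not remove bias if loss depends on current CRP.
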